1. PROJECT TITLE

A Randomized, Subject-Masked, Active-Controlled, Parallel-Arm Clinical Trial Comparing Pecs-2 and Paravertebral Nerve Blocks

4. ESTIMATED DURATION OF THE STUDY

Four years (1 month preparation, 36 months enrollment, 11 months publication prior to closure)

5. LAY LANGUAGE SUMMARY OR SYNOPSIS (no more than one paragraph)

Following painful surgical procedures of the breast, postoperative analgesia is often provided with a nerve block called a "paravertebral" block. For intense, but shorter-duration acute pain, a single-injection of numbing medicine is used which lasts about 12 hours. Recently, a new type of block has been reported: the "Pecs-2" block. The theoretical benefits include ease of administration since it is closer to the skin (less deep) compared with the paravertebral block and therefore easier to identify and target with ultrasound (therefore increasing success rate); and, a lower risk of complications. Lastly, it might be easier to insert a tiny tube which would allow additional numbing medicine to be injected. There are, therefore, multiple theoretical reasons to prefer the Pecs-2 over the paravertebral nerve block. Unfortunately, it remains unknown if the pain control provided by this new type of block is comparable to that provided with the older block. We therefore propose to compare these two blocks with a clinical study.

6. SPECIFIC AIMS

The overall objective of the proposed research is to determine the relative risks and benefits of Pecs-2 versus paravertebral blocks for single-injection local anesthetic administration.

Hypothesis 1: Following breast surgery, **analgesia** will be non-inferior in the recovery room with a Pecs-2 block compared with a paravertebral block as measured with the Numeric Rating Scale.

Hypothesis 2: For breast surgery, **opioid** consumption will be non-inferior in the operating and recovery rooms with a Pecs-2 block compared with a paravertebral block (primary: cumulative intravenous morphine equivalents).

Primary end point: *In order to claim that Pecs-2 blocks are non-inferior to paravertebral blocks, both Hypotheses 1 and 2 must be at least non-inferior.*

7. BACKGROUND AND SIGNIFICANCE

Following painful surgical procedures of the breast, postoperative analgesia is often provided with a paravertebral nerve block (PVB). For intense, but shorter-duration acute pain, a single-injection of local anesthetic is used with a duration of approximately 12 hours. The PVB has several limitations: it can decrease blood pressure, and very rare—but serious—complications have occurred, including

neuraxial injection, neuraxial hematoma, and pleural puncture.¹ An alternative block has been described: the Pecs-2 block.² The theoretical benefits include ease of administration since it is a plane superficial to the PVB and therefore easier to identify and target with ultrasound (therefore increasing success rate); and an increased safety margin: there are few anatomic structures in the immediate area which could be injured with the needle.³ To date, 7 randomized trials involving Pecs-2 block have been published, all involving mastectomy and a placebo control, and concluded that the Pecs-2 block does, in fact, provide post-mastectomy analgesia compared with a placebo control.⁴ Six of 7 studies reported no related adverse events. In one trial the occurrence of a hematoma and/or bleeding in three patients (2%) was reported, but it was unclear if these were related to the nerve block or a surgical complication. Of note, our proposed study includes subjects having breast surgery other than mastectomy, which has not been previously investigated (and also uses an active control—the paravertebral block—compared with placebo controls). Lastly, the plane may be easier to catheterize for continuous peripheral nerve blocks relative to the relatively-small volume PVB.⁵

There are therefore multiple *theoretical* reasons to prefer the Pecs-2 block. Unfortunately, it remains unknown if the analgesia provided by this new technique is comparable to that provided with the PVB.¹ We therefore propose to compare these two techniques with a randomized, subject-masked, active-controlled, parallel-arm, human subjects clinical trial.

8. PROGRESS REPORT

There are no preliminary or pilot study data.

9. RESEARCH DESIGN AND METHODS

This investigation will be a randomized, subject-masked, active-controlled parallel-arm, human subjects clinical trial. Of note, we will be using standard-of-care local anesthetic under an FDA-approved purpose and do not plan to research a possible change of indication or use of these medications as part of this research project. The treatments in both groups are currently used at our institution and there is true clinical equipoise at this time. The only difference in treatment between subjects who enroll versus those not enrolled in this study will be those who enroll will have the decision between which anatomic block location determined randomly, as opposed to the physician simply choosing him/herself.

Enrollment. Consenting adults undergoing breast surgery with a planned single-injection regional analgesic will be offered enrollment. Patients undergoing breast surgery with a planned perineural catheter regional analgesic will be excluded. Study inclusion will be proposed to eligible patients prior to surgery. If a patient desires study participation, written, informed consent will be obtained using a current UCSD IRB-approved ICF. Selection for inclusion will not be based on gender, race, or socioeconomic status. The study population of interest includes men and women of all races and socioeconomic status. Inclusion and exclusion criteria are listed in section #9 below.

Preoperative Procedures. Following written, informed consent, we will collect baseline anthropomorphic information (e.g., age, sex, height, and weight). All subjects will have a peripheral intravenous (IV) catheter inserted, standard noninvasive monitors applied, supplemental oxygen administered via a nasal cannula or face mask, and placed in the sitting position. Midazolam and fentanyl (IV) will be titrated for patient comfort, while ensuring that patients remain responsive to verbal cues. Both possible block locations will be viewed with ultrasound. If one or both of the locations is unacceptable for block placement in the clinician's opinion, the subject will not be

randomized and will not proceed further with the study.

Subjects will then be randomized using a computer-generated list and opaque, sealed envelopes to one of two treatment groups: (blocks of 4, stratified for unilateral vs. bilateral surgery): (1) Pecs-2 or (2) paravertebral block. All blocks will be placed by a regional anesthesia fellow or resident under the direct supervision and guidance of a regional anesthesia attending (or by the attending themselves).

For paravertebral blocks, a total of 18 mL of ropivacaine 0.5% with epinephrine will be administered per side (90 mg). An equivalent mass of ropivacaine will be administered for the Pecs-2 blocks (90 mg), but since more volume is required (30 mL per treated side), the concentration will be decreased to 0.3% ropivacaine (with epinephrine). Therefore, for bilateral procedures, 90 mg will be administered bilaterally. The area of needle insertion will be cleaned with chlorhexidine gluconate and isopropyl alcohol. All blocks will be placed using standard UCSD ultrasound-guided techniques as previously described.³

For Pecs-2 blocks and as described by Bashandy and Abbas,³ the needle will be advanced to the tissue plane between the pectoralis major and minor muscles at the vicinity of the pectoral branch of the acromiothoracic artery where 10 mL of local anesthetic will be deposited (Figs. 1-4). In a similar manner, 20 mL will be deposited at the level of the third rib above the serratus anterior muscle with the intent of spreading injectate to the axilla.

For paravertebral blocks, ropivacaine 0.5% 9 mL will be administered at each of two levels per side: the T3 and T5 levels for sides without axillary involvement; and at the T2 and T4 level for sides with axillary involvement.

[figure not shown]

FIGURE 1. Image of the probe position and needle direction from medial to lateral during Pecs I block.³⁰

FIGURE 2. Pecs I block ultrasound view. ax.a indicates axillary artery; p., pectoral branch of thoracoacromial artery.

FIGURE 3. Ultrasound image of needle tip at the plane of Pecs I block between the 2 pectoral muscles (arrows indicate the needle).³⁰

FIGURE 4. Local anesthetic spread between the 2 pectoral muscles. The arrow is pointing to the needle. LA indicates local anesthetic.

Single-injection blocks will be considered successful if, within 30 minutes, the subject experiences decreased sensation to cold temperature with an alcohol pad over the approximate level of the ipsilateral 4th thoracic dermatome. Misplaced blocks will be replaced successfully, or the patient excluded from further study participation. For subjects undergoing bilateral surgical procedures, a block using the same protocol will be administered on the contralateral side.

Intraoperatively, all subjects will receive a general anesthetic using inhaled and intravenous anesthetic and oxygen. Intravenous fentanyl will be administered for cardiovascular responsiveness to noxious stimuli at the discretion of the anesthesia provider.

Postop: Subjects will be discharged with a prescription for oxycodone 5 mg tablets for supplementary analgesia and instructed to record the time at which they take their first opioid tablet as well as the time at which they believe the block starts to wear off.

Outcome measurements (end points). Pain scores will be recorded using the NRS. Within the recovery room, pain scores, opioid requirements, and antiemetic administration will be recorded by nursing staff masked to treatment group. The morning following surgery, all subjects will be contacted by phone or in person [if hospitalized] to record lowest, average, highest, and current pain scores; sleep disturbances, and nausea using a 0-10 Likert scale (0 = no nausea; 10 = vomiting). For outpatients, opioid requirements will be recorded while inpatients will have opioid requirements extracted from the electronic medical record. In addition, we will extract antiemetic use from the electronic record. We will collect the times at which subjects felt their block resolve and they consumed their first opioid analgesic pills following recovery room discharge.

Hypothesis 1: Following breast surgery, **analgesia** will be non-inferior in the recovery room with a Pecs-2 block compared with a paravertebral block as measured with the Numeric Rating Scale.

Hypothesis 2: For breast surgery, **opioid** consumption will be non-inferior in the operating and recovery rooms with a Pecs-2 block compared with a paravertebral block (primary: cumulative intravenous morphine equivalents).

Primary end point: *In order to claim that Pecs-2 blocks are non-inferior to paravertebral blocks, both Hypotheses 1 and 2 must be at least non-inferior.*

Statistical methods. Descriptive statistics will be provided by arm and in aggregate. Baseline characteristics of arms will be compared using the Wilcoxon-Mann-Whitney and Fisher's Exact tests. Key characteristics that are significantly different ($p < 0.05$) will be included as covariates in the analysis models.

Primary aim. We will test the noninferiority of the serratus nerve block compared to the paravertebral nerve block. The 95% confidence interval (CI) associated with the Wilcoxon-Mann-Whitney test will be derived for the group difference (paravertebral minus serratus) in median pain scores within the recovery room. If the lower limit of the 95% CI is greater than -1.25, we will conclude noninferiority. If there are significant differences between the groups in any key characteristics, these characteristics will be included as covariates in a linear model. The same noninferiority margin (-1.25) will be applied to the 95% CI for the covariate adjusted group difference in mean pain derived from the linear model.

The noninferiority of the serratus nerve block with regard to total opioid consumption within the operating and recovery rooms will be tested in the same manner as pain, i.e. comparing the limits of a 95% CI associated with the Wilcoxon-Mann-Whitney test to a predefined noninferiority margin (in this case 2 mg). Covariate adjusted linear models will again be applied in the event that key characteristics are significantly different between the groups.

Sample size justification. Power for the Wilcoxon-Mann-Whitney derived noninferiority testing is based on 10,000 simulated trials. We simulated pain scores from a discrete distribution with median (interquartile range) 3 (2-5).⁶ Between the quartiles, the probability of each score was assumed constant. The distribution for each group was assumed to be the same. The sample size of n=50 per group provides 82% power to detect noninferiority in pain with a margin of 1.25. Similarly, opioid consumption was assumed to follow a truncated normal distribution with mean 2.5 mg and standard deviation 2 mg, and minimum value 0 mg. The sample size of n = 50 per group provides at least 95% power to detect noninferiority with margin 2 mg. However, to account for any unanticipated increase in variability, we will enroll 25 additional subjects in each treatment group. Therefore, we will enroll 75 subjects for each of the two treatments with primary end point values for a total enrollment of 150 subjects with a primary end point. To allow for dropouts, we request a maximum enrollment of 175 subjects. Noninferiority in pain is tested first, and if significant, noninferiority in opioid consumption is tested. Under this hierarchical testing framework, no adjustment in alpha is necessary to control Type 1 error.⁷

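### Does the absence of described masking steps, for the injection site or for the intraoperative anesthesia provider, require a change to the plan?

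*Combined protocol and SAP*

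**What the plan says.** The masking claim appears three times: in the title (Section 1), "A Randomized, Subject-Masked, Active-Controlled, Parallel-Arm Clinical Trial Comparing Pecs-2 and Paravertebral Nerve Blocks"; at the end of Section 7, "We therefore propose to compare these two techniques with a randomized, subject-masked, active-controlled, parallel-arm, human subjects clinical trial"; and at the start of Section 9, "This investigation will be a randomized, subject-masked, active-controlled parallel-arm, human subjects clinical trial". In each place it names subjects and nobody else.

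Section 9 then describes conduct. Under Preoperative Procedures the subject sits and is sedated, "while ensuring that patients remain responsive to verbal cues". Before randomization, "Both possible block locations will be viewed with ultrasound". The assignment comes from opaque sealed envelopes. On the block team, Section 9 says: "All blocks will be placed by a regional anesthesia fellow or resident under the direct supervision and guidance of a regional anesthesia attending". Alternatively, an attending may place the block. For Pecs-2, "the needle will be advanced to the tissue plane between the pectoralis major and minor muscles". For paravertebral block, "ropivacaine 0.5% 9 mL will be administered at each of two levels per side". Block success is judged in both arms by a cold test at the same thoracic dermatome.

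General anesthesia follows, with fentanyl given at the provider's discretion in response to cardiovascular signs. Under Outcome measurements, the nurses who record recovery-room pain, opioids and antiemetics are stated to be masked. Opioid given in the operating room counts toward Hypothesis 2, and Hypotheses 1 and 2 must both succeed.

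**The concern.** The two blocks are placed at visibly different sites, and the subject is awake enough to answer. Envelopes conceal the assignment only until they are opened. Section 9 mentions no sham puncture, drape, matching dressing or instruction to withhold the assignment, so the means of subject masking is not stated. The same is true of the nurse masking. The provider giving discretionary fentanyl may or may not know the block, and that fentanyl enters a primary endpoint.

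The stake is real in principle. Recovery-room pain is self-reported, part of the opioid total reflects a clinician's judgment, and both endpoints must pass. Expectation that differed by arm could cost the trial a correct claim. If it favored Pecs-2 while that block was truly worse by about the margin, it could help produce a false one.

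**Working it through.** **1. What is promised and what is described.**

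| Person | Masking stated? | What Section 9 provides |
|---|---|---|
| Subject | Yes | Sedation; both sites scanned before assignment; same cold test in both arms; general anesthesia before outcomes are scored |
| Recovery-room nurse | Yes | The statement itself; no method |
| Intraoperative anesthesia provider | No | Nothing; membership of the block team not stated |

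The first two rows lack detail about a masking the plan already requires. The third row contradicts nothing.

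**2. The plan's own power figures.** Inputs from Sample size justification and Primary aim: pain median 3, quartiles 2 and 5, margin 1.25; opioid mean 2.5 mg, SD 2 mg, minimum 0, margin 2 mg; two-sided 95% Wilcoxon-Mann-Whitney interval. The simulated rule is that the lower Hodges-Lehmann limit for paravertebral minus Pecs-2 must exceed minus the margin. At 50 per arm with equal arms:

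- Pain: 80.4–87.4% over three readings of the discrete distribution. The stated 82% lies in that range.
- Opioid: above 99.9%, consistent with the stated minimum of 95%.

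**3. Assumed shifts at 75 per arm.** The documents give no bias, so every shift is an assumption. The net excess is the average amount by which Pecs-2 appears worse; for example, 0.25 points means one Pecs-2 subject in four scoring 1 point higher. Ranges cover three readings of each distribution.

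| Net pain excess (points) | Pain test passes |
|---|---|
| 0 | 93.4–96.6% |
| 0.25 | 83.8–88.9% |
| 0.5 | 68.0–74.4% |
| 0.75 | 47.6–52.9% |
| 1.0 | 28.8–31.1% |
| 1.25 | 11.3–11.8% |

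| Net opioid excess (mg) | Opioid test passes |
|---|---|
| 0 | 100% |
| 0.5 | over 99.7% |
| 1.5 | 37.8–44.2% |
| 1.75 | 14.2–15.0% |
| 2.0 | 2.0–2.6% |

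Normal-approximation check for opioid: if 2.5 and 2 are the parameters before truncation at 0, the SD after truncation is 1.677 mg. Then SE = 1.677 × √(2/75) = 0.274 mg, and the pass probability is Φ((2 − net excess)/SE − 1.96).

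- Net 0.5: Φ(1.5/0.274 − 1.96) = Φ(3.5), above 99.9%.
- Net 1.75: Φ(0.25/0.274 − 1.96) = Φ(−1.05), about 15%.
- Net 2.0: Φ(−1.96) = 2.5%.

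**4. Reading the tables.**

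- *Provider.* With equal arms, a 0.5 mg distortion does not matter. Opioid error rises only if Pecs-2 is truly worse by about 2 mg and the distortion also favors it: 0.25 mg takes the false-pass rate from 2–3% to 14–15%, and 0.5 mg to 38–44%. No text supports either premise.
- *Subject.* With equal arms the opioid test passes about 100% of the time, so the joint claim is sensitive mainly through pain. A shift against Pecs-2 costs power; it does not create a false claim.
- *The 11–12% baseline.* At a true excess of 1.25 points, shifts of 0.25 and 0.5 in favor of Pecs-2 raise the pass rate to 29–31% and 48–53%. Yet the baseline already exceeds the nominal 2.5% with no masking shift. Integer scores give integer limits, so exceeding −1.25 means reaching −1 or higher. That excess comes from pairing integer scores with a fractional margin, not from masking.

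**5. What each possible remedy would do.**

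- *Matching dressings after surgery* cannot undo what a responsive subject perceived during placement. They would mainly support nurse masking, which is already stated. The Pecs-2 site is on the operated side, and the documents do not show whether a study dressing there suits the surgical field.
- *Withholding the block from the anesthesia provider* has a cost. Section 7 says paravertebral block can lower blood pressure, and Section 15 covers hypotension and pleural puncture. Whether that provider should know the site is a matter of care and handover, not only of bias.
- *Rewording the masking statement* would describe conduct better but would leave the design, data and analysis the same.

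**The case for a change.** The strongest contrary case is that writing down the means would cost almost nothing. If concealment steps exist locally, a sentence records them; if they do not, the label claims more than is delivered. One primary endpoint is self-reported, the nurses who record it are called masked without explanation, and a modest assumed shift in pain scores removes 8 to 10 percentage points of power (96.6 − 88.9 = 7.7; 93.4 − 83.8 = 9.6). Lack of evidence of bias is not evidence that there is none.

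Part of this stands. The description is incomplete, and a reader cannot tell from it how well subjects were masked. What does not follow is that the plan produces a wrong result. Subjects compare two active treatments, which Section 9 declares to be in equipoise, so no one expects a placebo. Section 9 defers block technique to institutional standards that are not reproduced, and the consent pages were removed from the text available, so the absence of any concealment step cannot be established. The tables would look the same for any distortion of the same size, whatever its cause.

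**Conclusion.** No change to the plan. The masking of subjects and recovery-room nurses is stated; its means is a gap in description that the study team can fill in conduct and the trial report can describe. The provider's knowledge of the block is outside the declared masking, and restricting it is a fair trade-off to leave as it is.

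No bias is demonstrated, and its size and direction cannot be derived from the documents. At 75 per arm under the plan's distributions and equal arms, an assumed 0.5 mg shift leaves the opioid pass rate above 99%. An assumed 0.25-point shift against Pecs-2 gives a pain pass rate of 84–89%, compared with 93–97% without it. This rests on three things: reading the label as covering subjects only, taking the nurse-masking statement at face value, and treating the shifts as illustrations. Evidence from conduct that subjects or nurses routinely knew the assignment would affect how the results are interpreted, but nothing in the documents indicates that.

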12. INFORMED CONSENT

If a patient desires study participation, written, informed consent will be obtained. An investigator or

research assistant/coordinator (including regional anesthesia fellows) specifically trained in both study details and appropriate consenting procedures will attain verbal and written informed subject consent. The method of documenting consent will be using written informed consent form (including a written HIPAA consent form and UCSD Experimental Subjects' Bill of Rights). Due to the fact that nearly all qualifying patients will be relatively healthy and all will be undergoing relatively minor ambulatory surgical procedures, the overwhelming majority will not be seen in preoperative clinic on a day prior to the day of surgery. Therefore, the study will be proposed the day of surgery in the preoperative area of the outpatient center (KOP) after patients present for their procedure. Patients will not be rushed into making a decision regarding the study, and this is possible since (a) patients are brought to the center with far more time than necessary to ensure no surgical delays and (b) this is a relatively simple, straight-forward study with no medical/health risks and therefore should not be a particular burden on prospective subjects. There will be approximately 20-40 minutes available for counseling subjects about the study and obtaining written informed consent before administration of sedation in the preoperative area.

Following informed consent and the signing of the UCSD IRB-approved ICF and HIPAA documents, these documents will be copied and the copy placed in the patient's medical record. The subject will be provided a copy along with the Subjects' Bill of Rights.

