14. POTENTIAL RISKS

The risks for both block locations include bleeding, infection, damage to nerves, inadequate pain relief, and injection into nearby structures including blood vessels, near or into spinal canal, and the lining of the lung. Currently, it remains unknown whether or not there are relatively higher risks with one anatomic location over the other. Given the proximity to the paravertebral, neuraxial, and pleural spaces, the risks of Pecs-2 and paravertebral blocks are felt to be similar. However, due to the increased distance between the Pecs-2 and the pleura and neuraxis, these risks are thought to be decreased with an improved safety margin. Although this speculation is hypothetical as no large series of ultrasound-guided Pecs-2 blocks have been published, there is the possibility that a patient's risk might be affected by study participation if the attending physician would have chosen one of the two possible blocks, while the randomization indicates the other be used. There is, however, the risk of loss of confidentiality with study participation.

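### Block size is fixed at 4 and printed in the protocol, and an opinion-based exclusion comes just before allocation: vary the sizes and withhold them

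*Combined protocol and SAP*

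**What the plan says.** Section 9 (Research Design and Methods) allocates subjects from a computer-produced list in opaque sealed envelopes, using "blocks of 4, stratified for unilateral vs. bilateral surgery". It gives one block size and does not mention varying it or keeping it from anyone.

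Three other statements bear on who could use that information:

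- **Consent.** Section 12 allows consent to be taken by an investigator or a "research assistant/coordinator (including regional anesthesia fellows) specifically trained in both study details and appropriate consenting procedures".
- **Block placement.** Section 9 states: "All blocks will be placed by a regional anesthesia fellow or resident under the direct supervision and guidance of a regional anesthesia attending". Attendings may also do this without a trainee. The two arms use different injection sites, so whoever places the block knows the arm. The stated masking covers subjects and recovery-room nurses.
- **Exclusion before allocation.** After consent, both sites are viewed with ultrasound. "If one or both of the locations is unacceptable for block placement in the clinician's opinion", the subject is not randomized. Randomization is the next step.

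The document does not say whether the envelopes are numbered, who holds the list, whether consenting staff are told the block size, or whether subjects dropped at the ultrasound step are logged.

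**The concern.** In a 1:1 block of 4, the last assignment is always determined by the first three, and the third is determined whenever the first two match. Opaque envelopes do not prevent that inference. Here one role may take part in enrollment and also know the assignments it carried out, and a discretionary exclusion falls at the moment when a forecast of the next arm would be useful.

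If a borderline ultrasound view were judged more strictly when one arm was expected, the arms could differ in anatomy or expected difficulty. Both noninferiority comparisons (pain and opioid use) rely on the arms being comparable. Analysis could not reliably repair such a difference. The planned adjustment applies only when key characteristics differ at p < 0.05; those "will be included as covariates in the analysis models". The baseline items named (age, sex, height and weight, given as examples) do not include ultrasound anatomy.

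**Working it through.** The document gives no predictability figure, so there is none to reproduce.

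**Inputs**

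- Block size 4 and two strata: section 9, randomization.
- 1:1 allocation: inferred from 75 subjects per arm, section 9, sample size justification.
- 150 subjects with a primary end point and at most 175 enrolled: same place.
- 36 months of enrollment: section 4.
- Split between unilateral and bilateral surgery: not given. Splits of 75/75 and 120/30 are assumed.

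**1. Certain assignments, full history known.** The six equally likely orderings of AABB contain 2, 1, 1, 1, 1 and 2 forced positions. That is 8 of 24 = 33.3%. By position, the probabilities of certainty are 0, 0, 1/3 and 1, and (0 + 0 + 1/3 + 1)/4 = 1/3.

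**2. Best-guess accuracy, full history known.** By position: 1/2, 2/3, 2/3 and 1. The mean is (1/2 + 2/3 + 2/3 + 1)/4 = 17/24 = 70.8%, against 50% by chance, an excess of 20.8 points.

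**3. Over the trial.** Each complete block contributes 4/3 certain assignments. A remainder of three contributes 1/3, and a shorter remainder contributes none.

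- 75/75: 2 × (18 × 4/3 + 1/3) = 48.7.
- 120/30: 30 × 4/3 + 7 × 4/3 = 49.3.

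Across 20,000 simulated lists the 95% ranges were 43–54 and 44–55. At 175 enrolled, the expected number is 57 to 58 for splits from 50:50 to 90:10.

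**4. Partial observer.** Suppose each earlier allocation was seen with probability p and the position in the block is known. Position 3 is certain if both earlier allocations were seen and match: p² × 1/3. Position 4 is certain if both allocations to the arm already filled were seen: p². The average is (p²/3 + p²)/4 = p²/3. If the position is not known, a Bayes calculation over 40,000 simulated decisions gives no certain assignments.

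| Share seen (p) | Certain, position known | Guess, position known | Guess, position unknown |
|---|---|---|---|
| 0.75 | 18.8% | 64.6% | 63.4% |
| 0.50 | 8.3% | 59.9% | 58.9% |
| 0.25 | 2.1% | 55.4% | 55.3% |

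**5. How hard full tracking would be.** Accrual is 150/36 = 4.2 to 175/36 = 4.9 subjects a month, over two strata and several operators.

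**6. Alternatives, full history known.** For mixed sizes, the observer knows the set of sizes but not their order.

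| Scheme | Certain | Best guess |
|---|---|---|
| Fixed 4 | 33.3% | 70.8% |
| Fixed 6 | 25% | 68.3% |
| Fixed 8 | 20% | 66.6% |
| Random 4/6 (simulated) | about 5% | about 69% |
| Random 4/6/8 (simulated) | about 2.4% | about 68% |

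For random 4/6/8, stratum lengths from 30 to 150 gave 2.2–2.5% certain and 67.4–68.0% guessed correctly. Over 150 subjects, 2.4% is 3 to 4 certain assignments. The excess over chance falls from 20.8 to about 18 points.

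**The case against.** The strongest reply is that one third is a ceiling that nothing in the document shows anyone reaching. It needs one person who knows the block size and every earlier allocation in the stratum, sustained over 36 months. That person must also hold a preference, influence the ultrasound judgement, and apply unevenly a rule that excludes a subject if either site is unacceptable. The clinician who judges the view need not be the one who took consent, and trainees work under direct attending supervision. The plan also asserts equipoise: "The treatments in both groups are currently used at our institution and there is true clinical equipoise at this time". Varying the sizes barely reduces probable guessing, which is all that selection needs. No bias on the pain or opioid scale has been demonstrated, and silence about envelope custody in a short protocol proves little.

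Most of this stands, and it is why the point is only one to consider. The one-third figure is conditional, the partial-observer figures are lower, and neither the direction nor the size of any bias can be estimated. The objection still leaves the opening in place. A rule that is symmetric on paper does not govern how an opinion is applied. Overall equipoise can coexist with a preference for an individual patient, and section 14 contemplates a case "if the attending physician would have chosen one of the two possible blocks, while the randomization indicates the other be used". The limited effect on guessing is a reason to pair the change with a log rather than to keep a printed fixed size.

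**Conclusion.** The point holds as an inexpensive improvement to the allocation method, not as a finding of bias. The upper bound is 33.3% of assignments known in advance and 70.8% guessable. It assumes 1:1 blocks of 4, knowledge of the block size and a complete allocation history in the stratum. With half the history, 8.3% would be certain if the position in the block were known, and none if it were not. Whether anyone would have this information, and whether it would affect the ultrasound exclusion, cannot be determined from the document.

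**What to change.** 1. Generate the list with randomly varying block sizes, for example 4, 6 and 8, within the existing two strata.
2. Remove the sizes from the protocol text. Keep them and the list in a restricted document held by someone who neither enrolls patients nor places blocks.
3. As a supplement, record each ultrasound acceptability decision in a screening log before the envelope is opened. Report the number of exclusions at that step, with reasons, by stratum. The log should be separate from the study records, because section 16 identifies those by randomization number and subjects dropped before randomization would presumably have none. The log makes selection visible; it does not prevent it.

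**Cost.** One regenerated list, one restricted document with a named holder role, and one log. No dose, eligibility criterion, sample size or analysis changes.

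The largest possible end-of-list imbalance rises from 2 to 4 per stratum. Simulated mean imbalance (8,000 lists per length) is:

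| Stratum length | Random 4/6/8 | Fixed 4 |
|---|---|---|
| 75 | 1.08 | 1.00 |
| 100 | 0.54 | 0 |
| 150 | 0.55 | 0.67 |

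Imbalance above 2 occurs in about 0.3% of lists at even lengths and 4% at length 75. Even the worst case, 4 in each of two strata in the same direction, would give 79 against 71. The variance factor would be (1/79 + 1/71)/(2/75) = 1.003, a negligible loss of precision.
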